10.5. Visit 6 (Week 12)

Visit 6 should occur after 12 weeks of double-blind study drug treatment, scheduled at Day 84 -5 / +7 days. The following assessments and procedures are to be completed in the following general order:

- Collect study drug and assess compliance
- Assess occurrence of adverse events
- Update concomitant medications
- Obtain vital signs and weight
- Administer CAPS-5-“Symptom Severity Version” using 1-week recall
- Conduct urine pregnancy test (for women of child-bearing potential). Serum pregnancy test may be done at Investigator’s discretion.

- Draw samples for clinical laboratory tests for:
 - Chemistry and hematology
- Perform visual examination of oral cavity
- Have the patient complete the following outcome scales (in order):
 - SDS
 - PROMIS scale for sleep disturbance
 - MTRSS (assessment of sedation)
 - PGIC
 - CSFQ-14
 - BDI-II (needs to be completed prior to the C-SSRS and reviewed by the C-SSRS rater at outset of C-SSRS interview)
- Administer C-SSRS-Since Last Visit Version
- Physician to assess CGI-I (needs to be completed once all other assessments are available for investigator to review)

10.5.1. Early Termination (ET)

In accordance with the Declaration of Helsinki, patients have the right to withdraw from the study at any time for any reason, and they will be advised of this right. The investigator and Tonix also have the right to remove patients from the study. Specific reasons for removal of a patient from the study could include, but are not limited to:

- An adverse event (AE)
- An illness that, in the judgment of the investigator or Tonix, might invalidate the study results or place the patient at risk
- The request of the patient, investigator, or Tonix, whether for administrative or other reasons
- Pregnancy

This study will attempt to obtain as complete information as possible on all participating patients. An effort must be made to contact the medical monitor prior to any patient's early termination. Each reason for early termination will be adjudicated. Patients who wish to terminate their participation in the study should be instructed to come to the clinic for an Early Termination Visit. The purpose of the Early Termination visit is to obtain critical information about the patient's participation, and should be scheduled preferably before there has been a substantial lapse in study medication usage. However, even if there has been a medication lapse, the patient should be encouraged to return to the clinic for this visit, and should be instructed to return all study medication. NOTE: These visit procedures are not intended for patients who fail to qualify for randomization or for any other reason withdraw from the study prior to receipt of a dose of double-blind study drug.

If the patient withdraws prior to the week 2 (visit 3) visit window (before day 11), the following assessments and procedures are to be completed at this visit in the following general order:

- Document reason for early termination
- Collect study drug and assess compliance
- Assess occurrence of adverse events
- Update concomitant medications
- Obtain vital signs and weight
- Conduct urine pregnancy test (for women of child-bearing potential). Serum pregnancy test may be done at Investigator's discretion.
- Draw samples for clinical laboratory tests for:
 - Chemistry and hematology
- Perform visual examination of oral cavity
- Have the patient complete the following outcome scales (in order):
 - MTRSS (assessment of sedation)
 - CSFQ-14
 - BDI-II (needs to be completed prior to the C-SSRS and reviewed by the C-SSRS rater at outset of C-SSRS interview)
- Administer C-SSRS – Since Last Visit Version

If the patient withdraws after the week 2 (visit 3) visit window (on or after day 11), the following assessments and procedures are to be completed at this visit in the following general order:

- Document reason for early termination
- Collect study drug and assess compliance
- Assess occurrence of adverse events
- Update concomitant medications
- Obtain vital signs and weight
- Administer the CAPS-5-“Symptom Severity Version” using 1-week recall
- Draw samples for clinical laboratory tests for:
 - Chemistry and hematology
 - Serum pregnancy test (for women of child-bearing potential)
- Conduct visual examination of oral cavity
- Have the patient complete the following outcome scales (in order):
 - SDS
 - PROMIS scale for sleep disturbance

- MTRSS (assessment of sedation)
- PGIC
- CSFQ-14
- BDI-II (needs to be completed prior to the C-SSRS and reviewed by the C-SSRS rater at outset of C-SSRS interview)
- Administer C-SSRS- Since Last Visit Version
- Physician to assess CGI-I (needs to be completed once all other assessments are available for investigator to review)

Once these assessments have been completed, the patient may be discharged from the study, provided that there is no need for additional follow-up to continue to monitor an adverse event or other condition.

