9.2. Dosing Instructions

Patients will be instructed to take **two** tablets of their assigned study drug (TNX-102 SL 2.8 mg tablets or placebo tablets) sublingually, placed simultaneously **under the tongue**, each evening at bedtime starting at bedtime on evening of Day 0 (Day of Visit 2) and continuing without interruption for 12 weeks. The study drug should be taken at bedtime after teeth brushing and other oral care has been completed. The mouth/sublingual area should be moist at the time of dosing, so the patient should drink a few sips of water prior to dosing, especially if prone to dry mouth. Patients will be instructed to place the two SL tablets under their tongue and keep them there until they have dissolved. They should not swallow, crush or chew the tablets. Patients should not eat or drink (or chew gum) for at least 15 minutes after dosing, and preferably not until morning. Patients will be reminded that only 2 (two) tablets are allowed per day. Note: In the event that the patient misses a dose, instruct the patient to continue dosing with two (2) tablets the next evening; i.e., they should not take more to make up for the missed dose.

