13.1. Populations for Analysis

The following populations will be defined for use in analyzing the efficacy and safety data in the study (see SAP for more details):

- Safety Population (SAFETY): All patients who receive at least 1 dose of study drug. All safety analyses and demographic/baseline characterization will be performed using this population, analyzed as treated, using the highest dose they were issued at any visit.
- Modified Intention-to-Treat Population (mITT): All randomized patients who have at least a baseline and one post-baseline CAPS-5 assessment. This is the primary population for efficacy analyses and patients will be analyzed based on their randomized treatment. See [Section 10.5.1](#) for early termination assessments.

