#### **7.1.2 Data Handling for Participants Who Discontinue Study Drug or Withdraw from the Study**

Participants who withdraw/drop out from the study will have their ET visit data collected included in the analysis based on the closest visit window (Week 4, 8 or 12). Visit windows will be assigned by splitting the periods between visits at the midpoint between the visits. If more than one record falls within the window, the one closest to the target date will be used in the analysis.

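### The Early Termination scale list follows the day of withdrawal, not the day of the visit, so some patients who could be scored on the CAPS-5 are not, and leave the primary analysis

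*Protocol*

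**What the plan says.** Protocol 10.5.1 splits the ET visit into two branches.

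- Early branch: "If the patient withdraws prior to the week 2 (visit 3) visit window (before day 11), the following assessments and procedures are to be completed". The list has safety items, MTRSS, CSFQ-14, BDI-II and C-SSRS. It has no CAPS-5, SDS, PROMIS, PGIC or CGI-I.
- Late branch: "If the patient withdraws after the week 2 (visit 3) visit window (on or after day 11"). This list adds all five scales, including "Administer the CAPS-5-“Symptom Severity Version” using 1-week recall".

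Both branches turn on when the patient withdraws; no rule uses the date of the visit. The two dates can differ, because the section also says that "even if there has been a medication lapse, the patient should be encouraged to return to the clinic for this visit". The schedule in Appendix 1 has no ET column that would settle the matter.

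The primary efficacy population in Protocol 13.1 is "All randomized patients who have at least a baseline and one post-baseline CAPS-5 assessment", and that section refers the reader to 10.5.1 for ET assessments. SAP Section 6 uses the same definition. Under SAP 7.1.2, ET data are "included in the analysis based on the closest visit window (Week 4, 8 or 12").

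**The concern.** One post-baseline CAPS-5 admits a patient to mITT, and the first scheduled one is at Visit 4. For anyone who leaves before Day 11, the ET visit is the only chance to obtain it. The checklist therefore decides who enters the primary analysis, even when the patient is in the clinic and the scale could be scored.

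Nothing later repairs this. The multiple imputation in SAP 9.1.1 is confined to mITT. The two MNAR sensitivity analyses in SAP 9.1.2 repeat the primary analysis, and the MAR model only removes the imputation step. SAP 7.1 presents efficacy tables for mITT, so these patients would not appear as non-responders on the CAPS-5 binary endpoints either. Both key secondary endpoints, CGI-I and SDS total, are lost for them as well.

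What is at stake is exclusion after randomization that may depend on treatment, for example through early tolerability. The SAP has a specific imputation rule for exits due to adverse events, lack of efficacy or loss to follow-up, but that rule cannot reach a patient who never enters mITT.

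**Working it through.** **1. The Day 11 cut-off.** Visit 3 is at Day 14 ± 3 (Protocol 10.3), so its window is 14 − 3 = 11 to 14 + 3 = 17. Day 11 reproduces as the start of that window.

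**2. First scheduled post-baseline CAPS-5.** Visit 4 is at Day 28 ± 5 (Protocol 10.4): Days 23-33. A patient who withdraws before Day 11 cannot have had one.

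**3. When a one-week recall is wholly post-dose.** Dosing begins "starting at bedtime on evening of Day 0 (Day of Visit 2"). A visit on Day v looks back over the nights of Days v − 7 to v − 1. All follow the start of dosing if v − 7 ≥ 0, that is, v ≥ 7. Same-day ET visits on Days 7, 8, 9 and 10 qualify, which is 4 of the 10 days from Day 1 to Day 10.

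**4. Effect of a gap between withdrawal and visit** (withdrawal on Days 1-10):

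| Gap (days) | Withdrawal days with visit on Day 7 or later | Withdrawal days with visit on Day 11 or later |
|---|---|---|
| 0 | 7-10 | none |
| 1 | 6-10 | 10 |
| 3 | 4-10 | 8-10 |
| 6 | 1-10 | 5-10 |
| 7 | 1-10 | 4-10 |

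None of these patients gets a CAPS-5 under the present rule.

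**5. Number affected.** The documents give no early-exit rate. Assume 2-6% in each arm of 275: 2 × 275 × 0.02 = 11, and 2 × 275 × 0.06 = 33. If withdrawals are spread evenly over Days 1-10, every patient attends and visits are same-day, a Day 7 rule recovers 40%: 4.4 to 13.2, about 4-13 patients. Incomplete attendance lowers this; later visits raise it.

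**6. Direction.** For illustration, assume mean improvements of 14 (drug) and 11 (placebo) among the other patients, a difference of 3.0, and no change in early exits. With exit fractions pD and pP, counting every early exit gives 14(1 − pD) − 11(1 − pP). Counting only the 40% recovered replaces each p by r = 0.4p / (1 − 0.6p).

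| Exit rate, drug / placebo | All early exits counted | Only the recovered 40% counted |
|---|---|---|
| 4% / 4% | 13.44 − 10.56 = 2.88 | 2.95 |
| 4% / 2% | 13.44 − 10.78 = 2.66 | 2.86 |
| 6% / 3% | 13.16 − 10.67 = 2.49 | 2.79 |
| 2% / 4% | 13.72 − 10.56 = 3.16 | 3.07 |

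The shift goes either way, depending on which arm loses more.

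**7. Power.** The sample-size assumptions are redacted. If 275 per arm gave 90% power, losing 2% or 5% leaves 89.4% or 88.5%; if 80%, then 79.2% or 78.0%. Lost power is the lesser issue.

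**The case against.** The strongest defence is that Day 11 is prespecified, applies equally to both arms and is openly cross-referenced from the mITT definition. The section prefers an ET visit before any substantial lapse, so most visits should fall close to the withdrawal. The documents do not define withdrawal, and a site could take it to mean the ET visit date. A score after a lapse is post-dose but not necessarily on treatment, and a Day 7-10 score carried as Week 4 data may say little about Week 12. Finally, the exclusion itself comes from the mITT definition.

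Much of this stands. It narrows the point without removing it. If withdrawal is read as the visit date, visits from Day 11 on are covered but Days 7-10 are not, and the fact that two readings are possible is itself a reason to state the rule. The late branch already accepts scores after a lapse.

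A reader might also infer four stronger things that the documents do not support.

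- *That these patients give no efficacy data.* BDI-II is on the short list and is a secondary efficacy endpoint, and the endpoint-specific inclusion rule in SAP 9.2.1 could admit it.
- *That withdrawals on Days 11-17 also get the short list.* The bracketed day limits are exhaustive and place these patients in the late branch. Read without the brackets, the words would leave Days 11-17 with no list, since those days are neither before nor after the Visit 3 window.
- *That the plan favours the drug.* No direction can be shown.
- *That the SAP would treat every early exit as unchanged from baseline.* Its baseline-based imputation covers only three reasons for discontinuation and conditions on observed post-baseline values; other exits are imputed under MAR within treatment group.

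**Conclusion.** The point holds in a limited form. The ET list is chosen by day of withdrawal. As a result, some patients who attend when a CAPS-5 could be scored get none of the five scales and leave mITT, and no planned analysis restores them.

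The size is not in the documents. About 11-33 patients of 550 would exit before Day 11 if the rate were 2-6% per arm, and only those attending an eligible ET visit are recoverable (about 4-13 under the even-spread, same-day, full-attendance assumptions). The 14 and 11 point improvements are also assumed and show only that the effect on the estimate has no fixed sign. This is a worthwhile, inexpensive improvement to a rule that controls entry to the primary analysis. It is not evidence of bias.

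The wording of the late branch needs reconciling in its own right, because a window of Days 11-17 cannot be over on Day 11.

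**What to change.** In Protocol 10.5.1:

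- Select the ET list by the date of the ET visit.
- Give the CAPS-5 (one-week recall), SDS, PROMIS, PGIC and CGI-I at any ET visit with a full recall week after the first dose, that is, Day 7 or later. At minimum, apply the existing Day 11 cut-off to the visit date.
- Replace the two descriptions of the late branch with a single day rule.

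In SAP 7.1.2, add a sentence on how ET scores before Day 14 (the midpoint of Day 0 and Day 28) map to Week 4. ET scores from Days 11-13 already raise this question. The sentence should say which day numbering it uses, since the SAP datasets call the protocol's Day 0 Day 1.

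The cost is one protocol edit, one SAP sentence, and one interview with short forms at a visit that already takes place, using raters and scales already in the study. The downside is that a few early, possibly off-drug scores are carried in the Week 4 window. Patients who are never seen, or are seen only before the cut-off, stay excluded by the mITT definition.

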10.5.2. Unscheduled Visits

Patients may need to be seen at other times than the scheduled study visits for additional safety assessments or to follow-up, as medically necessary, on clinical laboratory results, physical examination, or other findings. If an additional study visit is warranted, or occurs, the date and nature of the visit will be documented in the CRF and in the source documents.

Patients who call to report an oral AE that is a lesion of some form should be brought back to the clinic for an unscheduled oral exam if deemed appropriate. In the case in which the AE is solely sensory in nature (such as oral hypoaesthesia) *and* the patient reports there is no discernable associated lesion, an unscheduled oral exam is not required but may be arranged if the investigator determines it to be clinically appropriate.

10.6. Pharmacogenomic Assessment (Post-Study)

For patients who participated in P301 and are invited back to the site for participation in the optional pharmacogenomics assessment after having finished their participation, the patients will be invited in for an unscheduled visit in which they first will learn about the pharmacogenomics study and sign a separate written pharmacogenomics informed consent form. Next, a blood sample is drawn and processed for pharmacogenomic analysis. Once completed, the patient is discharged from the pharmacogenomics portion of the study.

11. STUDY ASSESSMENTS

11.1. Screening Assessments

11.1.1. Psychiatric and Medical History

A psychiatric interview using the Mini International Neuropsychiatric Interview (M.I.N.I.-Version 7.0.2) and a comprehensive medical history will be obtained at screening in order to determine whether the patient is eligible for enrollment.

While patients with mild traumatic brain injury (TBI) are eligible to participate in the study, moderate and severe TBI are excluded. Mild TBI (or concussion) is one of the most common forms of combat-related injury. Based on self-report data, approximately 15% of troops engaged in active combat in Afghanistan and Iraq may have suffered a mild TBI (Hoge et al., 2008). A *history of TBI* is defined as any traumatically induced structural injury and/or physiological disruption of brain function as a result of an external force that is indicated by new onset or worsening of at least one of the following clinical signs, immediately following the event:

1. Any period of loss of or a decreased level of consciousness;
2. Any loss of memory for events immediately before or after the injury;
3. Any alteration in mental state at the time of the injury (e.g., confusion, disorientation, slowed thinking);
4. Neurological deficits (e.g., weakness, balance disturbance, praxis, paresis/plegia, change in vision, other sensory alterations, aphasia) that may or may not be transient;
5. Intracranial lesion.

Although *severity of TBI* depends in part on patient assessment in the days after a traumatic head injury, for the purposes of this protocol, mild TBI is defined as:

1. Normal structural brain imaging findings
2. Loss of consciousness not greater than 30 minutes after injury
3. Alteration of consciousness not greater than 24 hours after injury
4. Posttraumatic amnesia not more than 24 hours after injury
5. No ongoing neurological deficits (Note: tinnitus, headaches, or sleep disturbances that appeared to result from the head trauma would *not* be considered as ongoing neurological deficits and therefore should *not* be interpreted as meaning the person has a greater severity than mild TBI.)

In addition, the past medication history will be reviewed. Any psychiatric medication or PTSD therapies utilized during the patient's lifetime should be collected. Responses from the M.I.N.I. will serve to document the presence of other psychiatric conditions. The diagnosis and severity of PTSD will be based on the CAPS-5 (Section 11.2.1).

11.2. Efficacy Assessments

The primary efficacy endpoint and many of the secondary and exploratory efficacy endpoints in this study are derived from clinician-administered assessments which must be administered by qualified and trained individuals at each clinical site. Study specific training will be required before staff is allowed to administer these scales. In an attempt to minimize variability in

responses of a given patient over time, it is important that the same rater administer the scales to a given patient throughout the study unless absolutely unavoidable due to the rater's absence from the clinic. It is also important that the assessments, including those that are patient-completed, be conducted in the specified order, according to specific instructions, and in a setting where the patient has minimal distractions, appropriate privacy and sufficient time to complete them.

11.2.1. Clinician-Administered PTSD Scale (CAPS-5)

The primary efficacy endpoint is the change from baseline (Visit 2) in total CAPS-5 score at Week 12 (Visit 6).

The CAPS-5 is an updated and validated version of a semi-structured interview that has been designed to assess the essential features of PTSD as defined by the DSM-5 (Weathers et al, 2013). The CAPS-5 affords the clinician flexibility to inquire about symptoms and diagnostic status over different time frames, such as past week, past month, and/or worst month for lifetime. For this study, a "Diagnostic" version of the CAPS-5 (lifetime and past month recall) will be utilized at the Screening visit to confirm the diagnosis of PTSD and determine eligibility based on symptom severity. A "Symptom Severity" version of the CAPS-5 (past week recall) will be completed by clinician at all other time points (Baseline [Visit 2] and after 4, 8, and 12 weeks of treatment [Visits 4, 5, and 6]). A CAPS-5 total score of 33 or above at both Screening ("Diagnostic" version) and Baseline ("Symptom Severity" version) is requisite for eligibility.

In addition to the total symptom score, the CAPS-5 affords the opportunity to examine clusters of symptoms, including Criterion B (intrusion symptoms), Criterion C (persistent avoidance), Criterion D (negative cognitions and mood), and Criterion E (arousal and reactivity), all of which will be secondary efficacy endpoints.

The CAPS-5 interview contains the following components:

- Life Events Checklist for DSM-5 (LEC-5): Completed by the patient at Screening Visit 1 only) and reviewed by the rater of the CAPS-5 interview at the start of the interview.
- PTSD Symptoms
 - Criterion A: the rater will review the patient-completed LEC-5 and then inquire into the qualifying index trauma (Criterion A) utilizing the study-specific Criterion A - Assessment Form (CA-AF) (Visit 1 only)
 - Criterion B: Items 1-5
 - Criterion C: Items 6-7
 - Criterion D: Items 8-14
 - Criterion E: Items 15-20
 - Criterion F: Items 21-22
 - Criterion G: Items 23-25
 - Global ratings: Items 26-28
 - Dissociative symptoms: Items 29-30

Further instruction on when to complete each component will be provided in the study specific versions of the CAPS-5 forms.

The LEC-5, which documents the patient's lifetime traumatic experiences, will be completed by the patient at Screening Visit 1 before the clinician administered CAPS-5. The CAPS-5 rater will be responsible for reviewing the answers on this form with the patient as part of the completion of the CAPS-5 Criterion A - Assessment Form in order to determine if the traumatic experience qualifies the patient for inclusion in the study. NOTE: If worst month lifetime PTSD symptoms resulted from earlier trauma(s), such as trauma(s) before age 18 or trauma(s) not related to military services, the prospective patient should be excluded from participation.

At Screening, the total CAPS-5 score (Diagnostic version with 1-month recall) must be ≥ 33 and must meet the other diagnostic criteria specified in Inclusion Criterion 2 ([Section 8.2](#)) in order for the patient to continue. At Baseline (Visit 2), the total CAPS-5 score (past week recall) must again be ≥ 33 .

The CAPS-5 interview must be completed by a qualified and trained rater. This rater should be kept consistent for a given patient throughout the study. If circumstances require non-conformity with the single rater approach for any patient, this should be documented. Additional information regarding the conduct, rating, and scoring of the CAPS-5 instrument as well as the requirements for rater training will be provided separately.

